Data analysis	
Patient characteristics at baseline will be summarized and presented.
 
The analysis will include calculation of unique incidence rates (with 95% CI) and incidence proportions of each reported term of non-serious AE (moderate and severe) and SAE. A patient may contribute with multiple events of the same AE term. AE specific incidence rates and proportions will be presented overall for the whole study period and also by time windows defined with reference to the first dose of Kineret following a SJIA diagnosis. Analyses of sub-populations with long-term Kineret treatment will enable descriptive comparisons of incidence early in the treatment cycle and incidence resulting from long-term treatment.
 
This study will pay a special interest to the incidence of MAS. Therefore, the time to event since start of Kineret treatment, in this scenario regardless of whether the patient was on Kineret treatment when the event occurred, and the cumulative probability of a first MAS event over time will be analyzed. Trigger events associated with each MAS episodes will be summarized.
 
Summary statistics for the duration of Kineret treatment will be presented overall and by time window.
 
The reasons for Kineret treatment discontinuation will be summarized with number and percentage. Use of other SJIA related medications at baseline and concomitantly with Kineret treatment will be summarized by treatment patterns.

Milestones	
The data extraction from the Pharmachild JIA registry is planned to start in March, 2019 and end in April, 2019. A final study report is planned for October, 2019.

4 Amendments and updates

None.

5 Milestones

This PASS is based on secondary use of data, utilizing already available data from the Pharmachild JIA registry. In the Pharmachild registry data has been collected since 2011. Data collected up until September 30, 2018 will be used in this study. The data extraction from the Pharmachild registry will start as soon as the CSP, SAP and contract with PRINTO have been finalized.

Milestone	Planned date
Start of data collection	March, 2019
End of data collection	April, 2019
Registration in the EU PAS register	March, 2019
Final report of study results	October, 2019

6 Rationale and background

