8.7 Data analysis

Patient characteristics at start of Kineret treatment will be summarized and presented.

There will be five main analysis sets:

- The complete set, including all patients with SJIA in the registry who have received Kineret at least once following a diagnosis of SJIA as per investigator judgement and enrolled before the cut-off date for the current study (September 30, 2018).
- The long-term treatment set-12, including those patients from the complete set with 12 months or more of continuous Kineret treatment *.
- The long-term treatment set-18, including those patients from the complete set with 18 months or more of continuous Kineret treatment *.
- The long-term treatment set-24, including those patients from the complete set with 24 months or more of continuous Kineret treatment *.
- The MAS-1 set, including patients with SJIA who have been diagnosed a first time with MAS following start of Kineret treatment

*For the long-term treatment set-12, 18 and 24 the longest continuous treatment period will be considered for inclusion in the sub-population. Hence, an index date may be set for patients who stopped Kineret treatment and later restarted and remained on treatment for a longer period than the previous.

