8.7.1 Incidence rates of Adverse events

The analyses will include calculation of unique incidence rates (with 95% CI) of each reported non-serious AE (moderate and severe), SAE and MAS as an ESI respectively. A patient may contribute with multiple events of the same AE term. Incidence rate of events (calculated as the number of the incident events divided by the sum of patient years under risk) will be expressed

as incidence rate per 100 patient years. The incidence rate will be derived by a Poisson regression model (with only intercept) and the 95% CI will be estimated using the Poisson estimator with a cluster-robust estimate of variance to control for both overdispersion and intracluster correlation. AE specific incidence rates will be presented overall for the complete study period and by time windows defined with reference to baseline. The time windows will be defined as follows: 1-6 months, 7-12 months, 13-18 months, 19-24 months and >24 months of calendar time. AEs and patient-time will only be counted during Kineret treatment exposure that includes an additional period of 2 days (i.e. slightly longer than 5 half-lives in patients without renal impairment after treatment stop).

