8.7.2.2 Analysis of the duration until the incidence of MAS

The number of days from first injection with Kineret (baseline) until the first occurrence of MAS will be presented for the MAS-1 set. The number of MAS events and percentages will be presented grouped by simultaneous Kineret treatment (Yes/No) and days since first injection with Kineret treatment (1-30 days, 31-180 days, 181-365 and >365 days).

In addition, the time from discontinuation of Kineret until the first occurrence of MAS will be summarized for the MAS-1 set. The number of events and percentages will be presented grouped by “still treated” and subsequently 10 day intervals since discontinuation of Kineret.

In the time to event analyses, all MAS events occurring after baseline will be counted regardless of whether patients are under simultaneous Kineret treatment exposure or not. Notwithstanding, in reporting it will be indicated whether simultaneous Kineret treatment exposure was present at the occurrence of the event.

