8.7.3 Incidence proportions of Adverse events

The incidence proportion (i.e. risk) for each reported AE term will be calculated overall and within time windows by counting the number of patients experiencing the event at or after baseline divided with the number of patients treated with Kineret during the respective period. As regards to the calculation of time window specific incidence proportions, the start date will be set to equal the start date of the time window or when the patient start Kineret treatment within the time window. Only events that occur when patients are on Kineret treatment exposure (including an additional period of 2 days after treatment stop will be counted).

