8.9 Limitations of the research methods

An uncontrolled single-armed study design is the only feasible design in this non-interventional study since a fair comparator group would be difficult to introduce given the real-world practice of treatment regimen. Accordingly, the study design carries the general limitations inherent in an uncontrolled design regarding statistical analyses, interpretation, generalizability and conclusiveness. The incidence rates for AEs while exposed to Kineret may be under or overestimated because of exposure-related misclassification of patient-time. The direction of the bias will depend on the direction of the difference in true incidence in the non-exposed (all other treatment options) group vs. Kineret exposed group (e.g. a higher incidence in non-exposed vs. exposed will over-estimate the incidence rates for the Kineret treatment). The non-exposed patient-time will likely be a mixture of other SJIA-related medications. Misclassification of exposure is likely during non-registered short interruptions of Kineret treatment. Nevertheless, by using a validly conducted register study with the primary objective to research the adverse effects of JIA related medications and with granular recording of exposure time will alleviate the magnitude of the potential exposure misclassification bias.

The use of sub-populations with patients treated for a certain time may bias the comparisons since the selected patients may have been selected because of a relatively low incidence of adverse events before selection into the sub-population. The probability of experiencing an adverse event by chance may be increased following selection into the sub-population. A comparison with the incidence rate for the respective time window in the total population (the complete set) and not only the sub-population specific incidence rate will likely alleviate a more unbiased conclusion.

All patients in the Pharmachild registry with a diagnosis of SJIA (as per ILAR classification criteria) and who were ever treated with Kineret following the SJIA diagnosis will be included in

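### For patients who restart Kineret, the complete-set and long-term-set time windows run on different clocks, so the comparison offered against selection bias is not like with like

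*Protocol*

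**What the plan says.** **Complete set.** Section 8.7.1 presents rates "by time windows defined with reference to baseline", and the last three windows are "13-18 months, 19-24 months and >24 months of calendar time". The abstract gives the origin as "by time windows defined with reference to the first dose of Kineret following a SJIA diagnosis", and section 8.7.2.2 equates baseline with the first injection: "The number of days from first injection with Kineret (baseline) until the first occurrence of MAS". Off-treatment time is dropped from the numerator and denominator ("AEs and patient-time will only be counted during Kineret treatment exposure that includes an additional period of 2 days"), but nothing stops or resets the clock during a gap. For the window-specific proportions, section 8.7.3 adds that "the start date will be set to equal the start date of the time window or when the patient start Kineret treatment" within the window. As baseline is itself the first dose, a start inside a later window can only be a restart.

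**Long-term sets.** Section 8.7 uses the longest continuous course to decide membership of the 12-, 18- and 24-month sets, and "an index date may be set for patients who stopped Kineret treatment and later restarted" and then stayed on treatment longer than before. Section 8.7.4 allows gaps of up to 30 days within a continuous course. It reports the time after the threshold together with each earlier window, under the same labels as section 8.7.1.

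**The comparison.** Section 8.7.4 says the complete-set rates will be considered when the sub-population rates are interpreted. Section 8.9 concedes that the long-term sets may be selected for few early events and offers this as the remedy: "A comparison with the incidence rate for the respective time window in the total population". It does not mention that the origins can differ.

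**The concern.** Elapsed time since first dose and time on the current course agree only for a patient who has not restarted after a gap of more than 30 days. Section 8.7.5 expects such gaps, since it lets a patient contribute several discontinuations. For these patients, the complete-set window says how long ago Kineret was first given, while the long-term-set window says how far into a course the patient is.

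Two things are at stake. First, the complete-set >24-month rate may mix the opening months of restarted courses with time that is truly late in a course. Second, the plan has one stated safeguard against selection bias in the long-term sets, and it relies on equal labels meaning equal things. A difference between the two sets could come from the definitions alone and be read as selection, or it could hide selection that is present.

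**Working it through.** The protocol states no rate, restart frequency or sample-size calculation that bears on this, so there is no figure to reproduce. The check has three steps.

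**1. One hypothetical patient on each clock.** The patient is on Kineret in months 0-3, off in months 3-27 and on again in months 27-45. The second course lasts 45 - 27 = 18 months, so it is the longest and qualifies for the 12-month set. The 2-day extension is ignored. Entries are on-treatment months per window.

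| Clock | 1-6 | 7-12 | 13-18 | 19-24 | >24 |
|---|---|---|---|---|---|
| Complete set, from first dose (8.7.1) | 3 | 0 | 0 | 0 | 18 |
| 12-month set, from index date at month 27 | 6 | 6 | 6 | 0 | 0 |
| 12-month set, if the first dose were kept as origin | 0 | 0 | 0 | 0 | 18 |

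In the complete set, 18 months count as >24 months although no continuous course exceeds 18 months. In the 12-month set the same months, and any events in them, fill windows 1-6 and 7-12 and the first 6 months after the threshold. The third row shows why section 8.7.4 needs the later origin: with the first dose kept, the preceding windows it asks for would be empty for this patient.

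**2. Effect on the complete-set >24-month rate.** Let *f* be the share of >24-month patient-time that lies in the first 6 months of a restarted course. Let RR be the event rate in that time relative to later time on a course. Then

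observed rate / late-course rate = (1 - *f*) + *f* × RR = 1 + *f*(RR - 1).

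Both inputs are assumptions. For *f* from 0.05 to 0.30:

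- RR = 1: 1.00 throughout, so no numerical bias.
- RR = 2: 1 + 0.05 × 1 = 1.05, up to 1 + 0.30 × 1 = 1.30.
- RR = 4: 1 + 0.05 × 3 = 1.15, up to 1 + 0.30 × 3 = 1.90.
- RR below 1 (for instance, if those who restart tolerated the drug before): the ratio is below 1.

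**3. Where the effect lands.** A simulation used 20,000 patients per scenario. It assumed follow-up uniform over 12-120 months, exponential course lengths with mean 18 months, gaps uniform over 2-36 months, at most one restart, and 10 events per 100 patient-years after the first 6 months of any course.

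| Stoppers who restart | Complete-set >24-month rate, RR = 2 | Same, RR = 4 |
|---|---|---|
| 0% | 10.0 | 10.0 |
| 10% | 10.6 | 11.9 |
| 25% | 11.2 | 13.4 |
| 50% | 11.7 | 15.0 |

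In the 12-month set, every window after the first stays at 10. This follows from the set-up, because risk depends only on time since the course began. The simulation therefore shows which table moves, and is no estimate for this registry. With no restarts the two sets agree in every window.

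**The case against.** The strongest reply has four parts.

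- **Few patients may be affected.** The index date may be moved only for patients whose longest course is a later one; for everyone else in the long-term sets the origins coincide. This stands, and it limits the origin mismatch to those patients.
- **The complete-set windows are openly labelled as calendar time.** The early-versus-late comparison is assigned to the continuous-treatment sets, where time past the threshold cannot be the opening of a short restart. This also stands. A reader might infer that the plan's long-term rates are themselves inflated. The documents do not support that: the distortion falls on the complete-set calendar windows, not on the post-threshold rates in the long-term sets.
- **The comparison is descriptive and hedged.** There is no test or decision rule, and section 8.9 already admits the selection problem. This is true, but a descriptive safeguard still has to compare equivalent windows.
- **The statistical analysis plan may settle it.** The protocol does not say outright that the 8.7.4 windows run from the index date; that is inferred from what 8.7.4 asks for. But the calendar clock in 8.7.1 and the movable index date in 8.7 are both fixed in the protocol, so this is more than detail left for later.

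A reader might also conclude that the first qualifying course should replace the longest. That is a preference. The longest course serves the long-term objective, and a patient with a 13-month and then a 40-month course would otherwise have different index dates in the 12- and 24-month sets. Nor would windows of cumulative exposure cure the problem, since the first weeks of a restart could still fall in >24 months for anyone with enough earlier exposure.

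**Conclusion.** The mismatch is real and follows from the protocol's own definitions, but only for patients who restart after a gap of more than 30 days. Any such restart can put early course time into a late complete-set window. Where the restarted course is also the longest, the same patient-time carries different labels in the two tables that sections 8.7.4 and 8.9 set against each other.

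It is tempting to state a percentage by which the >24-month rate is too high. The protocol supports neither a size nor a direction: it gives no restart frequency and no ratio of early to late risk. The ratios above rest wholly on assumed values. At RR = 1 the rates are unbiased and only the labels mislead; below 1 the rate would be too low. The point is worth correcting because it undermines the stated remedy for selection bias. It does not invalidate the rates in the long-term sets.

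**What to change.** - For the comparison in sections 8.7.4 and 8.9, tabulate the complete-set rates, and the proportions of section 8.7.3, by time since the start of the current continuous course. Use the plan's 30-day gap rule and the same origin as the long-term sets.
- Show first courses and restarts separately. Otherwise re-exposure would simply be merged into months 1-6 of the complete set.
- Keep the calendar-time windows as an additional table.
- State in sections 8.7 and 8.7.4 that the long-term-set windows run from the index date.

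The cost is some extra programming and one more table. No new data collection is needed, as section 8.9 describes the exposure recording as granular. The restart rows may be sparse with about 300 patients. The table should be specified before extraction: section 8.6 provides only for summary output, so a reader could not rebuild it from the report.

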8.7.2 Additional analyses of the incidence of MAS

8.7.2.1 Analysis of first occurrence and recurrence of MAS

The incidence rate of MAS will also be analyzed with respect to 1st occurrence and recurrence respectively. The rationale for this is to account for a biological distinction in altered risk following a first event. For the analyses, the 1st occurrence of MAS is defined to occur at or after baseline regardless of whether the patient had a history of MAS or not. The patients included in the risk set for a 2nd occurrence of MAS are only those who had a 1st occurrence of MAS as defined above. Likewise, the patients included in the risk set for a 3rd occurrence of MAS are only those who had a 2nd occurrence of MAS etc. MAS events and patient-time will only be counted during Kineret treatment exposure that includes an additional period of 2 days after treatment stop.

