8.7.2.4 Trigger events of MAS

For each event of MAS collected as an ESI, a trigger event is recorded in the CRF. The following categories are possible to record: 'Disease flare', 'infection', 'changes of treatment' and 'other'. The 'other' field is supplemented with a free-text field. For the MAS-1 set, a summary table will present the number of MAS events and percentages per category. Depending on available data recorded in the free-text field for the "other" category, more categories may be added to the summary table. Reasons will only be presented for MAS events that occur when patients are on Kineret treatment exposure (including an additional period of 2 days after treatment stop).

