8.7.4 Incidence rates of Adverse events in sub-population

In a sub-population constituting those with more than 12 months of continuous treatment with Kineret, incidence rates of non-serious AEs of at least moderate severity, all serious AEs and MAS will be calculated for the time after 12 months and in addition incidence rates will be retrospectively derived for each preceding time window (i.e. 1-6, 7-12 months). Similarly, the analysis will also be performed for the subgroup of patients that have more than 18 (preceding windows to present: 1-6, 7-12 and 13-18 months) and 24 (preceding windows to present: 1-6, 7-12, 13-18 and 19-24 months) months of continuous treatment with Kineret respectively. These analyses will enable descriptive comparisons of incidence early in the treatment cycle and incidence resulting from long-term treatment. In the interpretation of the incidence rates calculated for the sub-populations, respective incidence rate for the total study population (the complete set) will also be taken into account. Interruptions of treatment, e.g. treatment holidays, will be allowed for up to 30 days with respect to the definition of continuous treatment. Neither AEs nor patient-time will be counted during the interruption.

Only events that occur when patients are on Kineret treatment exposure (including an additional period of 2 days after treatment stop will be counted.

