10.1.2 Serious adverse events (SAE)

An AE that meets one or more of the following criteria/outcomes is classified as serious:

- Death.
- An adverse experience that places the subject at immediate risk of death from the adverse drug experience as it occurred
- In-patient hospitalization or prolongation of existing hospitalization
- A persistent or significant incapacity or substantial disruption of the ability to conduct normal life functions
- A congenital anomaly or birth defect
- An event that, based on appropriate medical judgement, may jeopardize the subject and may require a medical or surgical intervention to prevent an outcome described above
- Cancer
- Overdose
- Suspected transmission of an infectious agent via the drug (e.g., any organism, virus, or infectious particle, pathogenic or non-pathogenic).
- Other

Although overdose, cancer and suspected transmission of an infectious agent via the drug are not always serious by regulatory definition, these events are handled as SAEs.

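### Adverse events other than MAS that start more than 2 days after Kineret stops enter no planned event table, and triggers of off-drug MAS are left out although the abstract promises them for each episode

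*Protocol*

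**What the plan says.** For the incidence rates, Protocol section 8.7.1 says "AEs and patient-time will only be counted during Kineret treatment exposure that includes an additional period of 2 days". The reason given is drug elimination: 2 days is "slightly longer than 5 half-lives in patients without renal impairment after treatment stop". Sections 8.7.3 (incidence proportions) and 8.7.4 (long-term sub-populations) repeat the limit. Section 8.7.4 adds, for treatment gaps of up to 30 days, that "Neither AEs nor patient-time will be counted during the interruption". Section 10.1.2 lists cancer among events that are not always serious by regulation and says "these events are handled as SAEs".

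For MAS, section 8.7.2.1 sets the same window for first and recurrent events: "MAS events and patient-time will only be counted during Kineret treatment exposure that includes an additional period of 2 days after treatment stop". Section 8.7.2.2 takes the opposite line for time to event: "all MAS events occurring after baseline will be counted regardless of whether patients are under simultaneous Kineret treatment exposure or not". It splits first MAS by simultaneous Kineret use and groups it by 10-day intervals since discontinuation. Section 8.7.2.3 then censors the Kaplan-Meier curve of first MAS 2 days after discontinuation.

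On triggers, the abstract (data analysis) says "Trigger events associated with each MAS episodes will be summarized", whereas section 8.7.2.4 says "Reasons will only be presented for MAS events that occur when patients are on Kineret treatment exposure", with the 2-day extension.

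**The concern.** The objective in section 7 is the long-term safety profile. A window set by elimination time suits reactions that need drug in the body. It does not suit events that are recognised late, of which cancer is the clearest example that the protocol itself names. If such an event starts after the drug is stopped, a reader of the final report would not learn that it happened.

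The trigger table raises a related problem. Change of treatment is one of the trigger categories that can be recorded. MAS episodes from day 3 after a stop are ones in which stopping Kineret could have been recorded as the trigger, and these are the episodes that the table drops.

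**Working it through.** **1. Counting window in each planned event analysis**

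| Protocol section | Analysis | Events counted |
|---|---|---|
| 8.7.1 | Rates of non-serious AEs, SAEs, MAS | On Kineret + 2 days |
| 8.7.2.1 | Rates of first and recurrent MAS | On Kineret + 2 days |
| 8.7.2.2 | Time to first MAS; time from stop to first MAS | Any time after baseline |
| 8.7.2.3 | Kaplan-Meier, first MAS | Censored 2 days after discontinuation |
| 8.7.2.4 | MAS triggers | On Kineret + 2 days |
| 8.7.3 | Incidence proportions of AEs | On Kineret + 2 days |
| 8.7.4 | Rates in long-term sub-populations | On Kineret + 2 days; nothing during interruptions |

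Six of the seven analyses stop at 2 days and one does not. The exception covers MAS only. For other AEs and SAEs the relevant sections are 8.7.1, 8.7.3 and 8.7.4, and all three stop at 2 days.

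**2. Three events, each with onset a week after a stop, followed through the plan**

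- *A cancer.* It is outside the window in 8.7.1, 8.7.3 and 8.7.4. Section 8.7.5 tabulates reasons for discontinuation, and an event that starts after the stop would not be one of them. Section 8.6 says that no patient listings will be obtained. The event is reported nowhere.
- *A first MAS.* It is shown in 8.7.2.2 as off Kineret and in the first 10-day interval. It enters no rate (8.7.1, 8.7.2.1), is censored out of the curve (8.7.2.3), and has no trigger shown (8.7.2.4).
- *A recurrent MAS.* It enters no rate and no trigger table. The displays specified in 8.7.2.2 are built around the first occurrence.

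**3. The 2-day figure**

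Two days is 48 h, and 48 / 5 = 9.6 h, so 2 days exceeds 5 half-lives if the half-life is below 9.6 h. The protocol gives no half-life, so its statement cannot be reproduced. By its own wording it applies to patients without renal impairment, while section 8.2 applies no exclusion criteria.

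**4. Direction of any effect on the rates**

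Let E and T be the on-treatment events and person-time, and e and t those in an added post-stop period. The planned rate is E/T and the extended rate is (E + e)/(T + t). The extended rate is higher only if e/t > E/T. The protocol gives none of these four quantities, so neither the sign nor the size of a difference follows from it.

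**The case against.** The 2-day window is stated in advance, has a reason, and defines a legitimate on-treatment rate. Section 8.9 says that unexposed time is likely a mixture of other SJIA medications. In a single-arm study, events counted long after a stop may belong to those treatments. That stands, and it is why the 2-day analysis should remain primary.

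Much that might seem lost is in fact counted. Late-onset events in patients still on Kineret fall in the window beyond 24 months and in the long-term sets. An infection that led to a hold would ordinarily have its onset before the hold, and section 10.2 records onset dates. Adverse events that led to a stop of more than 30 days appear among the discontinuation reasons in section 8.7.5. The gap is confined to onset more than 2 days after a stop, plus events during interruptions. The explicit interruption rule is written for the sub-populations in section 8.7.4.

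A reader might infer that MAS after withdrawal cannot be seen at all. The protocol does not support this: section 8.7.2.2 is designed to show it, and the MAS-1 set in section 8.7 has no on-treatment condition.

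It can also be said that supplementary windows belong in the SAP, which is not at hand. The point here is what the protocol fixes: sections 8.7.1 and 8.7.2.1 say that only on-treatment events count, and section 8.7.2.4 restricts the trigger table. An SAP that simply follows these sections reproduces the gap.

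**Conclusion.** The point holds within these limits. For AEs and SAEs other than MAS, no planned rate or proportion covers onset from day 3 after a stop, no listing fills the gap, and section 8.9 does not name it as a limitation. For MAS, first events after a stop are visible as counts and percentages, but without a person-time rate. Off-drug recurrences enter no rate, and the trigger table is narrower than the abstract says. Sections 8.7.2.2 and 8.7.2.3 also need reconciling. The former may mean only its own summaries when it speaks of time-to-event analyses, but as written it conflicts with the censoring rule.

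The number of events affected cannot be derived from the protocol. Two stronger readings are tempting and unsupported. One is that the SAE and MAS rates are biased low: events and person-time are removed together, so the result is a rate for a different period, with no known direction of difference. The other is that the omitted MAS episodes come mostly from treatment change: section 8.7.2.4 does not define that category as stopping Kineret, and it could cover other medication changes.

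The conclusion assumes that the registry holds events after Kineret stops. Section 10.2 (events recorded whether or not related to Kineret) and the post-stop table in section 8.7.2.2 both point that way.

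**What to change.** - Keep exposure plus 2 days as the primary on-treatment analysis in sections 8.7.1 to 8.7.4.
- Add a secondary tabulation of SAEs and MAS, including recurrences, with a longer post-stop window and person-time counted to match. Thirty days is one choice. It is the protocol's own boundary between interruption and discontinuation, not an established risk window. Include events and time during interruptions.
- Report cancer and death from first dose of Kineret to end of follow-up, labelled as including off-drug time and other treatments.
- In section 8.7.2.4, tabulate triggers for all post-baseline MAS, split by on and off Kineret, which also brings it into line with the abstract.
- Reconcile section 8.7.2.2 with the Kaplan-Meier censoring in section 8.7.2.3, and state which analyses the count-all rule governs.
- Name the 2-day limit in section 8.9.

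The cost is revised wording and some additional summary tables, specified before extraction. Section 10.2 shows that event descriptions, onset dates and MAS triggers are already collected. The output stays at summary level, so the arrangement in section 9.1 is unaffected. The downside is that the secondary tables mix in time on other SJIA medications, so they are supportive only and do not replace the on-treatment rates.
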